2.3.3 Secondary outcome analyses

- Proportion with parent entered data to track response to treatment

The dependent variable will be the proportion with parent entered data to track response to treatment as any Vanderbilts completed by the parent from date of medication start to 6 months post ADHD medication start date. Differences between intervention and control groups on this outcome will be evaluated using a logistic regression model. Potential covariates (e.g. baseline characteristics of age, race, with large differences between groups) will be included in a secondary analysis model evaluating the effectiveness of the intervention.

- Total number of measures completed by parents to track child response to treatment from date of medication start to 6 months post medication start
 - Measures completed are defined by completion of the Vanderbilt (VADPRS)

The dependent variable will be a count of the number of Vanderbilts completed by the parent from date of medication start to 6 months post ADHD medication start date. Differences between intervention and control groups on this outcome will be evaluated using a generalized linear model assuming a Poisson distribution with a log link function. The number of days from start of medication to end of study, 6 months post medication will be included in the model as an offset. Other potential covariates (e.g. baseline characteristics of age, race, with large differences between groups) will be included in a secondary analysis model evaluating the effectiveness of the intervention.

- Number of parent portal logins from registration to 6 months post mediation start

The dependent variable will be a count of the number of portal logins from date of study registration to 6 months post ADHD medication start date. Differences between intervention and control groups on this outcome will be evaluated using a generalized linear model assuming a Poisson distribution with a log link function. The number of days from portal registration to end of study, 6 months post medication will be included in the model as an offset. Other potential covariates (e.g. baseline characteristics of age, race, with large differences between groups) will be included in a secondary analysis model evaluating the effectiveness of the intervention.

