Official Title of the study: **Developing New Technologies to Improve ADHD Medication Continuity**

NCT number: **NCT02390791**

Document name: **Analysis Plan**

Date of the document: **11/1/17**

ADHD Enhanced Portal Statistical Analysis Plan

Prepared by: [name]

Date: 11/1/17

Analysis plan approved by:

[name], MEd, MSc
Associate Professor
Division of General and Community Pediatrics
PI ADHD Enhanced Portal Study

11/1/17
Date

The results of the ADHD Enhanced Portal Pilot study Aim 3 will be assessed as described in this document. This statistical analysis plan begins with an overview of the key components of the study including its design, objectives, and outcome measures. This is followed by a detailed description of the statistical analyses that will be utilized to address Aim 3 study hypotheses.

1. Overview of study: This study is a multi-practice, cluster randomized trial to evaluate the effectiveness of an Enhanced ADHD portal. Practices that agree to participate in the study were randomized 1:1 to receive either the intervention (enhanced ADHD portal) or the control group (standard portal) prior to subject enrollment. We used a covariate-constrained randomization procedure to ensure that the intervention and control practices were balanced with respect to: 1) number of health care providers and 2) average percentage of Medicaid patients (Ivers et al. 2012). We planned to enroll a total of 80 children newly diagnosed with ADHD from 8 practices in this trial (40 from the intervention practices and 40 from the control practices).

1.1 Study Objective: Evaluate the general effectiveness of the intervention (e.g. enhanced ADHD portal), compared to control (e.g. standard portal), on medication continuity as measured by prescription records and other more proximal outcomes during the first six months of treatment.

Working hypothesis 1: compared to the control group, the intervention group will have greater medication continuity as measured by number of days covered with medicine.

Working hypothesis 2: compared to the control group, the intervention group will have greater proportion with parent entered data to track response to treatment.

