1.2 Outcome measures

Primary

- Medication continuity as measured by number of days covered with medicine within 6 months of medication start.
 - Number of days covered with medicine is calculated from audit of prescriptions written during the first 6 months of treatment.

Secondary

- Proportion with parent entered data to track response to treatment
 - Entered data is defined by completion of at least one parent-completed Vanderbilt (VADPRS) between medication start to 6 months post medication start
- Total number of measures completed by parents to track child response to treatment from date of medication start to 6 months post medication start
 - Measures completed are defined by completion of the Vanderbilt (VADPRS)
- Number of family portal logins from date of registration to 6 months post medication start.

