1.4 Schedule of visits and time points of interest

- Registration on the portal (usually before consent)
- Consent date
- Baseline survey (baseline, after consent, usually a few days after)
- Medication start (varies by subject)
- 6 months post medication start, 6-month survey (completion)

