2.2.3 Completion

Patient will be considered to have completed the study once the patient completes the 6-month post medication survey or study end date on 9/24/17.

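### The any-Vanderbilt outcome for working hypothesis 2 makes no allowance for children whose follow-up closes at 9/24/17 before six months, although every count outcome does

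*SAP*

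**What the plan says.** - **Hypothesis.** SAP 1.1, working hypothesis 2: "compared to the control group, the intervention group will have greater proportion with parent entered data to track response to treatment".
- **Outcome.** SAP 1.2: "Entered data is defined by completion of at least one parent-completed Vanderbilt (VADPRS) between medication start to 6 months post medication start". No minimum period of observation is attached.
- **Model.** SAP 2.3.3, for this outcome: "Differences between intervention and control groups on this outcome will be evaluated using a logistic regression model". The only adjustment offered is a secondary model with baseline characteristics that differ markedly between groups.
- **End of follow-up.** SAP 2.2.3: "Patient will be considered to have completed the study once the patient completes the 6-month post medication survey or study end date on 9/24/17". SAP 1.4 notes that the medication start date differs between subjects.
- **Population.** SAP 2.2.2 takes in everyone who consented and started medication, whatever their length of follow-up.
- **Count outcomes.** For the number of Vanderbilts, SAP 2.3.3 states: "The number of days from start of medication to end of study, 6 months post medication will be included in the model as an offset". The primary outcome (2.3.2) and portal logins (2.3.3) also have a days offset.
- **Missing data.** SAP 2.2.5 does not impute secondary outcomes. Its examples of why they may be missing do not include closure of the study.

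**The concern.** The Vanderbilt count and the any-Vanderbilt indicator come from the same form, the same child and the same window. The plan adjusts the first for time observed and not the second. An offset running from medication start serves a purpose only if that time varies, so the plan recognises unequal follow-up and then leaves it out of the one outcome that tests working hypothesis 2.

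The chance of at least one completed form cannot fall as observation lengthens. If a child is cut off at 60 or 90 days without a form and scored no, the proportion reported is no longer a six-month proportion. With similar shares cut off in both arms, the main effect is dilution. With different shares, part of any difference between arms reflects when children started medication. Practices were randomised before subjects were enrolled, and the randomisation was constrained on provider numbers and Medicaid percentage (SAP 1), so it was not set up to balance start dates. With 8 practices, one that recruits late could shift an arm.

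**Working it through.** The SAP gives no expected proportion, effect size or power for this outcome, so there is no planned figure to reproduce. Everything after step 1 illustrates assumed inputs.

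**Inputs from the SAP:** closing date 9/24/17; window of six months from medication start; 40 children planned per arm.

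**Assumed inputs:** the six-month proportion p, a constant rate of first completion, and the share q of an arm cut off at day t. Six months is taken as 182 to 182.5 days, which makes no difference at the precision shown.

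**Step 1: who could be cut off.** Counting back 182 to 183 days from 9/24/17 gives 25 to 26 March 2017; six calendar months gives 24 March. A child who starts after late March 2017 cannot be observed for six months by the closing date.

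**Step 2: chance of a form by day t.** P(t) = 1 − (1 − p)^(t/182). With p = 60%:
- t = 60: 1 − 0.4^(60/182) = 26%
- t = 90: 1 − 0.4^(90/182) = 36%

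**Step 3: proportion shown by an arm.** (1 − q)p + qP(t). With p = 60% in both arms (no true effect):

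| Cut at | q = 10% | q = 30% | Spurious odds ratio |
|---|---|---|---|
| 90 days | 0.9 × 0.60 + 0.1 × 0.364 = 57.6% | 0.7 × 0.60 + 0.3 × 0.364 = 52.9% | 1.21 |
| 60 days | 0.9 × 0.60 + 0.1 × 0.261 = 56.6% | 0.7 × 0.60 + 0.3 × 0.261 = 49.8% | 1.31 |

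Over p = 40% to 80% and both cut-off days, the same split gives 1.16 to 1.48.

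**Step 4: milder inputs (p = 60%, cut at 90 days).**
- 5% v 15% cut off: 58.8% v 56.5%, odds ratio 1.10. For 10% v 15%: 1.05.
- 10% v 30% cut off, but 80% of eventual completers done by day 90 (0.8 × 60% = 48%): 58.8% v 56.4%, odds ratio 1.10. With 90% done by then: 1.05.

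**Step 5: equal shares with a true effect.** With 30% v 60% at six months and 10%, 20% or 30% of both arms cut at 90 days, the 30-point difference becomes 29.0, 28.0 or 27.1 points. Power with 40 per arm (two-sided 5% assumed, clustering ignored) goes from 78% to about 76%, 73% or 70%.

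**Step 6: treating the cut-off children without a form as missing.** If they are dropped while cut-off children with a form stay, the step 3 case at 90 days gives 0.576/(0.576 + 0.36) = 61.6% and 0.529/(0.529 + 0.28) = 65.4%. Both exceed the true 60%, and the false difference runs the other way.

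**The case against.** The strongest reply is that the text does not show that any child was cut off. The wording in 2.2.3, "completes the 6-month post medication survey or study end date on 9/24/17", may only close out children whose six months had passed without a returned survey, and the offset wording in 2.3.3 can be read as equating end of study with six months. The SAP gives no enrolment or start dates. This stands as to number, which could be zero. It does not remove the gap: if nobody could be cut off, the offsets running from medication start would be nearly constant and would do almost nothing.

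A reader might go further and infer that late starters *are* counted as failures. The SAP does not say so. Scoring them no follows most naturally from the definition in 1.2, but they could be handled as missing under 2.2.5, and no rule says which. Step 6 shows that dropping them would not be neutral either.

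A reader might also infer that the arm comparison *is* biased. That needs unequal shares cut off, for which there is no evidence. The 10% v 30% split (4 v 12 of 40) and the constant rate are chosen inputs, and step 4 shows how quickly the odds ratio falls towards 1. Even the 1.21 is small against sampling error: its logarithm is 0.19, against a standard error of about 0.45 with 40 per arm and clustering ignored, or 0.42 standard errors.

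Finally, 2.2.5 calls secondary outcomes supportive and exploratory, and the Vanderbilt count, which has an offset, is a partial check. Both points are fair and limit the weight of the concern.

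**Conclusion.** The inconsistency holds on the text: the SAP allows for follow-up shorter than six months in every count model and not in the yes/no outcome for working hypothesis 2. If some children are cut off and scored no, the reported figure understates the six-month proportion. A false difference between arms arises only if the shares cut off also differ. The illustrative odds ratio is about 1.21 under no effect, a constant rate, 60% at six months and 10% v 30% cut at 90 days. It is 1.05 to 1.10 under the milder inputs tried and up to 1.48 under the harsher ones. How many children were in fact affected cannot be told from the SAP. The point should be settled in the plan because this is the sole measure of a stated hypothesis, but it concerns a secondary outcome and leaves the primary analysis untouched.

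**What to change.** In SAP 2.3.3:

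1. Run the any-Vanderbilt logistic regression in children whose six months from medication start ended on or before 9/24/17. Select on start date alone, never on whether a form was completed.
2. Report the number of children cut off, by arm.
3. Show the all-subjects analysis as a sensitivity analysis, stating how cut-off children without a form are coded.

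The restriction needs no assumption about when forms are completed. A complementary log-log model with log days as offset is at most a further sensitivity analysis, because it builds in a constant rate of first completion. If 48% complete by day 90 and the true six-month figure is 60%, it extrapolates to 1 − 0.52^(182/90) = 73%.

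No change to 2.2.3 is needed: completion there is a status label, and none of the analyses in 2.3.2 to 2.3.4 selects on it.

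The cost is a few lines of text and the loss of a few late starters from one secondary analysis. The SAP is dated 11/1/17, after the closing date, so the children affected can be counted at once. If there are none, the result does not change.

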2.3.4 Intervention Fidelity measures

Intervention group only

The following will be summarized as count and percentage:

- Proportion of parents who completed the Shared Decision-Making component
- Proportion of parents who selected an outcome measure (defined as set a behavior to be tracked)
- Proportion of parents who entered monitoring data (defined as filled in behavior rating data)
- Proportion of parents who received text messages
- Proportion of parents who used the social forum (starting 3/6/16)

Associations between parent characteristics and intervention fidelity measures noted above will be evaluated using logistic regression models. Separate models will be utilized for each of the 5 fidelity measures listed above. The following variables will be included as independent variables in the logistic regression models:

- Parent Technology use
 - Measured at baseline and defined by use an app to track or manage health (yes/no)
- Primary Caregiver Parent Education
 - 3 levels: HS or less, some college (2 yr or tech), college grad or above
- Parent Numeracy
 - The Subject Numeracy scale measured at baseline
 - Continuous measure

Associations between the 5 intervention measures listed above and medication continuity (primary outcome) measure will be evaluated using the same approach described under the primary outcome analysis. Separate models will be utilized for each of the 5 fidelity measures listed above.

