2.2.2 Intent-to-Treat (ITT) Population

The ITT population is defined as all subjects who consented and started ADHD medication.

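### The five fidelity logistic models put about four slopes on some 40 parents with no small-sample estimator, so estimates may be inflated, or infinite for items met by few or nearly all parents

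*SAP*

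**What the plan says.** SAP section 2.3.4 restricts the fidelity analyses to one arm ("Intervention group only"). After the descriptive summaries it states: "Associations between parent characteristics and intervention fidelity measures noted above will be evaluated using logistic regression models". It adds: "Separate models will be utilized for each of the 5 fidelity measures listed above". The covariates are fixed: "The following variables will be included as independent variables in the logistic regression models". They are technology use (yes/no), education ("3 levels: HS or less, some college (2 yr or tech), college grad or above") and numeracy as a continuous score. There is no selection or reduction rule.

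The planned size is in section 1: "40 from the intervention practices and 40 from the control practices". Section 2.2.2 narrows the analysis set: "The ITT population is defined as all subjects who consented and started ADHD medication". If the fidelity models use that set, the usable number could fall below 40.

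Section 2.3.4 names no penalised or exact estimator, no minimum number of parents in the smaller outcome category, and no rule for separation or non-convergence. It gives no expected prevalence for any of the five items.

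**The concern.** With few parents in the smaller outcome category per slope, logistic regression fitted by maximum likelihood has two known problems. Finite slopes tend to lie too far from zero. And when some combination of covariates perfectly predicts the outcome for some parents (complete or quasi-complete separation), at least one estimate is infinite.

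Fidelity items are natural candidates for lopsided splits. Receiving text messages could be close to universal, and use of the social forum, counted only from 3/6/16, could be rare. That is a judgement about plausibility, since the SAP gives no figures. For such an item the odds ratios for who engaged with the portal could be overstated or not estimable, and the analyst would have to choose a fallback after seeing the data.

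**Working it through.** The SAP has no sample-size or precision figure for these models, so there is no figure of its own to reproduce.

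**Inputs from the SAP.** n = 40 planned in the intervention arm (section 1); five binary items; covariates as listed in section 2.3.4.

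**Slopes.** Technology use 1 + education 2 (three levels, categorical) + numeracy 1 = 4, plus an intercept.

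**Smaller-category parents per slope** = n × min(p, 1 − p) / 4, where p is the share of parents who met the item. At n = 40:

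| Prevalence p | Smaller category | Per slope |
|---|---|---|
| 50% | 20 | 5.0 |
| 30% or 70% | 12 | 3.0 |
| 20% or 80% | 8 | 2.0 |
| 15% or 85% | 6 | 1.5 |
| 10% or 90% | 4 | 1.0 |
| 5% or 95% | 2 | 0.5 |

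**Separation.** Simulated data sets were tested for complete or quasi-complete separation, in A and B by linear programming. All covariate distributions and effects are assumed:

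- Run A: 600 data sets per prevalence; technology use 50%, education 25/35/40%, normal numeracy, no true associations.
- Run B: 1,500 data sets per prevalence; technology use 40%, education 30/35/35%, standard normal numeracy, true log odds ratios 0.7, 0.5, 0.7 and 0.5. B was run at 5% to 50%; its low-prevalence results are set beside the matching high prevalence, which has the same smaller-category count.
- Run C: a further repeat at n = 40.

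| Prevalence | A | B | C |
|---|---|---|---|
| 50% | 1% | 1% | 1% |
| 70% (B: 30%) | 8% | 9% | 7% |
| 80% (B: 20%) | 20% | 26% | 22% |
| 90% (B: 10%) | 64% | 67% | 65% |
| 95% (B: 5%) | 91% | 79% | not run |

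At 15% prevalence B gave 43%. At 5%, a further 14% of B's data sets had no variation in the outcome at all. With n = 30, B gave separation in 4% at 50% prevalence, 18% at 30%, 46% at 20% and 76% at 10%.

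**Size of finite estimates at 50% prevalence.** A separate comparison in 1,500 data sets with a true log odds ratio of 0.69 gave a maximum-likelihood mean of 0.82 among converged fits: 0.82 / 0.69 = 1.19, or 19% too large. The bias is 0.82 − 0.69 = 0.13 against a standard deviation of 0.82, and 0.13 / 0.82 = 0.16, about one-sixth of a standard deviation. In B the four slopes averaged 1.20 to 1.25 times the truth; in C they were about 10-22% too large.

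**The same data fitted by Firth penalised likelihood.** In the 0.69 comparison the mean was 0.70 and the standard deviation 0.69. In B the mean slopes, as multiples of the truth, were 1.00-1.11 at 50% prevalence, 0.93-1.18 at 30%, 0.92-1.03 at 20%, 0.93-1.01 at 15% and 0.70-0.99 at 10%. Firth estimates are finite whenever both outcomes occur.

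**The case against.** Several points on the other side are fair, and most of them stand.

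- **The SAP does not write maximum likelihood.** It says only logistic regression, and a penalised fit is still logistic regression. Maximum likelihood is the default meaning when nothing else is named, but it is an inference. So is categorical coding of education, though it is the natural reading of three levels.
- **A reader might infer that the estimates will be inflated or infinite.** The document does not support that. It gives no prevalences, and for items met by 30% to 70% of parents separation is uncommon (1-9%). Nor is inflation uniform: in B, among non-separated data sets at 10-20% prevalence, education slopes averaged only 0.15-0.85 of the truth, because the samples with infinite education estimates drop out.
- **The bias is small beside the imprecision.** At one-sixth of a standard deviation, it would not be the main reason to distrust an odds ratio from 40 parents.
- **The largest separation figures fall where no model should be fitted.** With 40 parents, fewer than 5 in the smaller category means below 5 / 40 = 12.5%. At 95% prevalence, 0.95^40 = 13% of data sets would have no variation, and no estimator can help there. Where penalisation would be used, the risk is about 1-26% at 50-80% prevalence and 43% at 15% or 85%.
- **A reader might infer that the fidelity table would be unusable.** It would not be: section 2.3.4 already requires counts and percentages for every item. Section 2.1.1 also allows a justified deviation, though that choice would be made after seeing the data.

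What remains is that the plan fixes the covariates and sample for five models, one or more of which could plausibly fail, and gives no rule for that case.

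**Conclusion.** The point holds as a minor, low-cost improvement. With the planned 40 parents and four slopes, the default fit would give slopes about 10-25% too large even at the most favourable prevalence. The chance of at least one infinite estimate would rise from about 1% at 50% prevalence to 7-9% at 70%, 20-26% at 80% and about 65% at 90%.

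These figures rest on assumed item prevalences, covariate distributions and effect sizes, on maximum likelihood as the default reading, and on the planned rather than the achieved arm size. Fewer usable parents would make matters worse.

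The consequence is confined to the models for predictors of fidelity. These items are neither primary nor secondary outcomes in section 1.2, neither working hypothesis concerns their predictors, and the between-arm comparisons are unaffected.

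**What to change.** In section 2.3.4, state that the five models relating parent characteristics to fidelity will be fitted by Firth penalised likelihood with profile-likelihood confidence intervals, keeping education at three levels. Add that where fewer than about 5 parents fall in the smaller outcome category, only the counts and cross-tabulations will be reported.

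Education need not be collapsed to one ordered term. That would impose a linear trend across the levels, and in run B the four-slope Firth fit already averaged 0.92-1.18 of the truth at 15-50% prevalence.

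The cost is a few lines of SAP text and a different estimation option, with no new data. The downside is slight shrinkage toward the null for rare or near-universal items. It becomes noticeable at about 10% prevalence (0.70-0.99 of the truth), where about 4 of 40 parents are expected in the smaller category and the minimum-count rule would usually apply instead.

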2.3.1 Description of study population

Sample size:

The total number of subjects who are consented/registered and withdrawn will be given. A summary of subjects who were withdrawn will be provided.

Demographics and Clinical Characteristics, Patient and Parent:

Demographic and clinical characteristics as measured at baseline will be summarized by trial arm.

Variables to be summarized are: parent age, parent race and ethnicity, relationship to child, parent sex, parent marital status, parent education, technology use, parent numeracy score, child sex, child age, child race and ethnicity, child insurance. Variables will be summarized using descriptive statistics appropriate for each type of data item.

Baseline characteristics with large differences between groups will be included in analyses evaluating the effectiveness of the intervention.

Practice characteristics:

Practice characteristics measured prior to randomization assignment (start of study) including physician sex, physician race and ethnicity, physician age, years at practice, number of ADHD subjects seen per week will be summarized by trial arm. Variables will be summarized using descriptive statistics appropriate for each type of data item.

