2.3.2 Primary outcome analysis

Primary outcome: Medication continuity as measured by number of days covered with medicine within 6 months of medication start.

- Number of days covered with medicine is calculated from audit of prescriptions written during the first 6 months of medication treatment.

For the primary outcome, the dependent variable will be a count of the number of days covered with medicine within 6 months of ADHD medication start date. Differences between intervention and control groups on this outcome will be evaluated using a generalized linear model assuming a Poisson distribution with a log link function. The number of days from start of medication to end of study will be included in the model as an offset. Other potential covariates (e.g. baseline characteristics of child age, and race with large differences between groups) will be included in a secondary analysis model evaluating the effectiveness of the intervention.

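### The five fidelity–continuity models, run in the intervention group only, inherit a covariate rule based on imbalance between arms and so are unprotected against possible confounding by parent education and numeracy

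*SAP*

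**What the plan says.** Section 2.3.4 is restricted to the intervention group. It plans two sets of regressions.

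- **Fidelity on parent characteristics.** Logistic models, one per fidelity measure, with a fixed list introduced by "The following variables will be included as independent variables in the logistic regression models": technology use (yes/no), education (three levels) and numeracy (continuous).
- **Days covered on fidelity.** Five separate models with no covariate list of their own. They "will be evaluated using the same approach described under the primary outcome analysis".

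The approach referred to is in section 2.3.2: a "generalized linear model assuming a Poisson distribution with a log link function", with follow-up time as an offset and no covariates in the main model. On adjustment it adds: "Other potential covariates (e.g. baseline characteristics of child age, and race with large differences between groups) will be included in a secondary analysis model". The stated purpose of that second model is to estimate how well the portal works against control.

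Section 2.3.1 shows what the groups are: "Demographic and clinical characteristics as measured at baseline will be summarized by trial arm", and the rule about large differences follows in the same subsection. Education, technology use and numeracy are among the baseline variables listed there.

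**The concern.** Leaving covariates out of a main model is defensible when the exposure is randomised. Here the exposure is whether a parent completed the decision-making component, set a target behaviour, entered ratings, received texts or used the forum. Most of these are choices, and none is described as randomised.

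The inherited selection rule does not repair this. Inside one arm there is no arm contrast, so a rule that looks for imbalance between arms can bring in a variable unrelated to portal use and pass over one strongly related to it.

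If more educated or more numerate parents both use the components more and keep prescriptions going longer, the unadjusted model attributes that difference to the component. A component with no effect could then appear to go with better continuity, although the variables needed for a basic adjustment are already in the data set.

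**Working it through.** **1. Is there a figure in the plan to reproduce?** No. The SAP gives no sample size, power, alpha or expected effect for these models. The check is a reading of the text, followed by an illustration.

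**2. The text, side by side.**

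| Question | SAP 2.3.2 (source) | SAP 2.3.4 (where it is reused) |
|---|---|---|
| Contrast | Intervention against control | Fidelity yes against no, one arm |
| How exposure arose | Randomised by practice | Mostly parents' own behaviour |
| Main-model covariates | None | None, by reference |
| Secondary-model covariates | Those differing between arms | Same rule by reference; no arms to compare |

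Nothing in 2.3.4 redefines groups as users and non-users.

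**3. Size of a possible shift.** The only input from the document is the planned arm size (section 1: "40 from the intervention practices and 40 from the control practices"), so n = 40. The rest is assumed:

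- one binary parent characteristic, with prevalence *a* among users and *b* among non-users of a component;
- the characteristic multiplies expected days covered by *r*;
- the component has no effect (true rate ratio 1).

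The unadjusted rate ratio is then

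RR = [1 + a(r − 1)] / [1 + b(r − 1)]

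| r | a/b = 0.6/0.4 | a/b = 0.7/0.3 |
|---|---|---|
| 1.00 | 1.00 | 1.00 |
| 1.10 | 1.06/1.04 = 1.019 | 1.07/1.03 = 1.039 |
| 1.25 | 1.15/1.10 = 1.045 | 1.175/1.075 = 1.093 |
| 1.50 | 1.30/1.20 = 1.083 | 1.35/1.15 = 1.174 |

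If a = b the ratio is 1.00 whatever *r* is. Both links are needed for any bias. With an assumed 182-day window and half of it covered in the reference stratum (91 days), the extremes of the table are 91 × (1.06 − 1.04) = 1.8 days and 91 × (1.35 − 1.15) = 18.2 days.

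**4. Simulation of the specified model.** Further assumptions: 40 independent parents, half of them users, beta-binomial days (more variable than Poisson), 1,500 runs. A Poisson model with log link and offset was fitted with and without the characteristic. A rejection is a false positive at the nominal 5% level. Scaled means that the standard error was multiplied by the square root of Pearson chi-square over its degrees of freedom.

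| r, a/b | Unadjusted RR | Rejections, unscaled / scaled | Adjusted RR | Rejections, unscaled / scaled |
|---|---|---|---|---|
| 1.00, 0.5/0.5 | 0.997 | 68.1% / 5.0% | 0.997 | 69.0% / 5.3% |
| 1.00, 0.7/0.3 | 1.002 | 68.4% / 5.7% | 1.000 | 68.3% / 5.4% |
| 1.25, 0.6/0.4 | 1.048 | 68.3% / 5.9% | 1.002 | 65.5% / 4.9% |
| 1.25, 0.7/0.3 | 1.092 | 71.1% / 8.0% | 0.997 | 67.0% / 3.8% |
| 1.50, 0.7/0.3 | 1.182 | 83.5% / 23.3% | 1.001 | 63.1% / 4.5% |

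At a true 5%, the simulation error is about √(0.05 × 0.95/1500) = 0.6 percentage points.

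Adjustment brings the rate ratio back to 1.00 in every row. It brings the rejection rate near 5% only with scaled errors. With the unscaled model, the only one the SAP specifies, most runs reject a true null even with no confounding, and adjustment does not change that.

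**5. Cost in parameters.** Education (three levels) takes 2 degrees of freedom and numeracy 1: 3 of about 40. Technology use would add 1, making 4.

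**The case against.** The strongest reply is that the SAP promises associations, in a pilot, on measures that are neither primary nor secondary outcomes. A crude association described as such is not an error, and the plan states no causal or component-selection use. That stands, and it limits the point to the interpretation of supportive analyses. It does not rescue a covariate rule that has no relevant meaning in the group analysed.

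Other replies stand in part:

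- *The named characteristics are not barred.* They are among the section 2.3.1 baseline variables and could enter the secondary model if the arms happened to differ on them. That would be for a reason unrelated to portal use.
- *Not every measure is self-selected.* The SAP does not say whether receiving texts was the parent's choice.
- *Adjustment is thin and incomplete.* Three parameters are a real cost in 40 parents when a component has few users or few non-users, and unmeasured motivation would remain.

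A reader might infer more than the document supports. The SAP does not call education, numeracy or technology use drivers of fidelity; it plans to test whether they are associated with it. Nor does it follow that the five associations are confounded: that also needs a link with days covered, which the SAP neither states nor tests. And adding education would not by itself restore nominal error rates in the specified model, as the unscaled columns above show.

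**Conclusion.** The point holds as a specification weakness in supportive analyses. Section 2.3.4 borrows an adjustment rule made for a randomised contrast between arms and applies it to mostly self-selected behaviour within one arm. The five associations are left unprotected against possible confounding by parent characteristics that the trial already measures.

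The size is unknown. With no true effect, the unadjusted rate ratio could be about 1.02 to 1.18 if the characteristic multiplies days covered by 1.1 to 1.5 and its prevalence differs between users and non-users by 60/40 to 70/30. It is 1.00 if either link is absent. All of these inputs except n = 40 are assumptions. The randomised primary comparison is not affected.

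**What to change.** In section 2.3.4, replace the bare reference to the primary approach with text to this effect:

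> The between-arm imbalance rule does not apply to the fidelity–continuity models. Each of the five associations will be reported unadjusted and adjusted for parent education and numeracy, side by side, and interpreted as non-causal. Where users or non-users of a component are few, education will be collapsed, or the adjusted model will be treated as a sensitivity analysis.

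The plan should state beforehand what count is too few. Technology use is left out of the fixed set because section 1.4 puts portal registration usually before consent and the baseline survey after it. An answer about using a health app could therefore already reflect the portal. It could be added where it was recorded before registration.

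The cost is a few sentences, no new data, about 3 degrees of freedom of roughly 40 parents, and slightly wider intervals. The unadjusted estimates are kept, so nothing planned is lost.

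The change removes bias from the two measured variables only. No nominal error rate should be claimed for these models unless the Poisson standard errors are also scaled for overdispersion.
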